## **9.4 Demographic and Baseline Characteristics**

Patient characteristics will include the following:

- Patient demographics (age, gender; race, ethnicity)
- Medications
- Concurrent medical conditions
- Baseline PSA
- Prostate size, cancer staging, and Gleason score

## **9.5 Efficacy Analyses**

### **9.5.1 Primary Efficacy Outcome – Estimated Blood Loss**

The primary efficacy outcome is the estimated blood loss (EBL) during RALRP. The amount of EBL will be recorded in ccs, and the data will be summarized separately for both treatment groups, including 95% confidence intervals for the means. Treatment means will be compared using a matched pairs t-test.

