## **1.2 Status and Limitations of Current Therapies**

Current treatment options for localized prostate cancer include active surveillance, radiation therapy (delivered as external beam radiation or brachytherapy), and radical prostatectomy (1,4,13,14). No statistically significant survival advantage has been reported with any one treatment option compared to the others, and treatment decisions are based on patients' symptomatic burden, comorbidities, stage of disease, and probability of treatment side effects (1, 4, 13-16).

Among patients with high-grade localized prostate cancer, radical prostatectomy is associated with substantial increases in overall survival (17). Over the past decade, robotic-assisted laparoscopic radical prostatectomy (RALRP) has surpassed open retropubic radical prostatectomy (RRP) as the most common surgical treatment for prostate cancer. RALRP now accounts for 80% of all radical prostatectomies performed in the United States (18,19). Although long-term outcomes data following RALRP are limited, available evidence suggests that mortality outcomes following RALRP and RRP are comparable (both are extremely low), and that RALRP may be associated with lower complication rates (19-21). Both perioperative (blood loss and transfusion requirements, postoperative pain, length of hospital stay, and 30-day mortality) and long-term follow-up (potency, continence, quality of life, biochemical recurrence, salvage therapy requirements, and overall and disease-free survival) outcomes associated with RRP have been well characterized (19,22,23).

Although there is no universal definition of a "large" prostate – threshold values in the published literature range from 50 to 100g – there is general consensus that large prostate size poses a therapeutic challenge for both surgeons and radiation oncologists (24-26). Of particular relevance to RALRP, larger prostate size limits mobility and visualization, and have been associated with longer procedure times and increased blood loss during surgery (22,23,27). Patients with larger prostate sizes are also more likely to experience poor postoperative functional outcomes, typically requiring more time to regain continence and achieving poorer sexual function (22,24).

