### **3 PAE Patient Population**

#### **3.1 Inclusion Criteria**

Patients must meet all of the following inclusion criteria in order to be entered into the study:

1. Patient is 45-79 years old
2. Patient has signed informed consent
3. Patient must have biopsy-proven prostate adenocarcinoma with localized disease
4. Patient must be a candidate for robot-assisted radical prostatectomy (RALRP)
5. Patient has a prostate size >40 grams

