### 4.2 Control Patients

A similar cohort of patients who undergo RALRP without PAE will be treated as a matched control group. The controls will be matched using a 1:1 ratio to PAE treated patients based on AUA risk group. Risk stratification will be as follows, according to AUA guidelines:

- Low risk: Stage T1c to T2a tumors, AND PSA  $\leq 10$ ng/mL, AND Gleason score  $\leq 6$

- Intermediate risk: Stage T2b tumors, OR PSA > 10ng/mL but ≤ 20ng/mL, OR Gleason score 7
- High risk: Stage T2c or higher tumors, OR PSA > 20ng/mL, OR Gleason score 8-10

Control patients will be selected after 10 patients for the PAE arm have been identified, such that the first potential control patient who matches the risk score of a PAE patient and agrees to participate in the study is matched to the appropriate member of the PAE arm. Once a match is identified, additional matches for a single PAE patient will not be sought. Because we are matching PAE and control patients based on AUA risk score only, we do not anticipate difficulty in finding a matched control for every PAE patient.

Control patients will sign written informed consent before any study-specific assessments are performed. Patients will complete EPIC and IIEF questionnaires within 12 weeks prior to RALRP, and will undergo MRI as a baseline study. Oncologic and functional outcomes will be evaluated by assessing PSA, EPIC, and IIEF at months 3, 6, 9, and 12 post RALRP, and then annually per standard follow-up protocol for the treating institution.

Safety will be evaluated for PAE patients throughout the study treatment and assessment periods by assessing adverse events, concomitant medications, changes in laboratory values, and findings on physical examination. Safety will be evaluated for Control patients during RALRP and the follow up period by assessing adverse events and concomitant medications.

The patients in both groups will continue to be followed post RALRP according to standard follow up protocol for the treating institution.

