### **Control Patients (Visit -1 must be within 12 weeks prior to RALRP):**

Prior to RALRP patients in the Control group will have the following assessments performed:

- Obtain Informed Consent
- Medical History, including demographics
- Physical exam, including vital signs, height (baseline only), weight, and genitourinary evaluation
- Assessment that patient is a match for a PAE patient based on:
  - Low, intermediate or high risk prostate cancer based on AUA guidelines
- Recording of concurrent medical conditions
- Recording of current medications
- Prostate Specific Antigen (PSA)
- Urinalysis
  - Specific gravity, protein, glucose, blood, leukocytes, nitrites
- Baseline blood tests
  - Complete blood count (CBC) including red blood count (RBC), white blood count (WBC), platelets, hemoglobin, hematocrit, neutrophils
  - PT (Prothrombin Time)
  - Comprehensive metabolic Panel
- Expanded Prostate Cancer Index Composite (EPIC) Questionnaire
- International Index of Erectile Function (IIEF) Questionnaire
- Digital Rectal Exam (DRE) and TRUS of the prostate
- MRI of the prostate

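### The primary blood-loss comparison neither matches on nor adjusts for prostate size, and no size criterion is stated for controls

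*Combined protocol and SAP*

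**What the plan says.** All references are to the combined protocol and SAP.

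- **Primary test (9.5.1).** "Treatment means will be compared using a matched pairs t-test". No covariate or stratum term is named. Confidence intervals are planned for each arm's mean, not for the difference between arms.
- **Matching (4.2).** One variable with three levels is used: "Because we are matching PAE and control patients based on AUA risk score only". On timing, "Control patients will be selected after 10 patients for the PAE arm have been identified". A consenting control who "agrees to participate in the study is matched to the appropriate member of the PAE arm" forms the pair.
- **Size criterion (3.1).** "Patient has a prostate size >40 grams" stands in a section headed as the PAE population. The control checklist in 5.1, "Assessment that patient is a match for a PAE patient based on", names only the AUA risk level. Appendix A2 shows a matching assessment where Appendix A1 shows an eligibility assessment.
- **Size and bleeding (1.2).** "larger prostate size limits mobility and visualization, and have been associated with longer procedure times and increased blood loss during surgery".
- **Use of size in the analysis.** Section 9.4 lists it as a baseline characteristic, and 9.1 plans summaries by group. Section 9.5.3.1 plans MRI volume change for PAE patients only.
- **Status of the study (9.2).** It is a proof-of-concept study without a formal sample size calculation.

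**The concern.** The protocol itself names a predictor of the primary outcome and then leaves it out of both the matching and the analysis of a non-randomized comparison. On a plain reading of section 3 it also restricts that predictor in one arm. If PAE patients all have glands above 40 g and controls need not, the PAE arm starts with larger glands and so, by section 1.2, with more expected bleeding. An unadjusted difference in mean EBL would then understate any benefit of PAE.

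The baseline table would show a size gap, but 9.5.1 plans nothing that acts on it. In a study meant to decide whether the idea deserves further work, missing a real benefit is the costly error.

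**Working it through.** **Stated figures.** There is no power, effect size, EBL SD or alpha to reproduce. Two-sided 0.05 is assumed throughout.

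**Degrees of freedom.** The paired test on 10 pairs has 10 − 1 = 9 (critical t 2.262). A model with treatment and three risk groups has 20 − 4 = 16 (2.120). Adding volume leaves 15 (2.131).

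**No size gap.** For a 1.2-SD benefit the noncentrality is 1.2/√(2/10) = 2.683. If risk group does not predict EBL, power is 66.7% paired and 71.2% for the risk-group model.

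**Size of a possible gap.** Assume control gland size is normal and PAE size follows the same distribution cut at 40 g. If a share s of control candidates lies at or below 40 g, the mean gap is φ(z)/(1 − s) SD, where z is the s-quantile:

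- s = 10%: 0.1755/0.90 = 0.195 SD
- s = 25%: 0.3178/0.75 = 0.424 SD
- s = 50%: 0.3989/0.50 = 0.798 SD

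**Bias.** Bias in EBL SD units is correlation × gap. At s = 50% it is 0.1 × 0.798 = 0.08, 0.3 × 0.798 = 0.24 and 0.5 × 0.798 = 0.40, all against PAE.

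**Power at a 1.2-SD benefit.** These come from simulation with a 3/5/2 risk-group split and risk group not prognostic. Cells show paired test / risk-group model / model with volume, in %, and are good to about one point.

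| Size–EBL correlation | s = 10% | s = 25% | s = 50% |
|---|---|---|---|
| 0.1 | 65 / 70 / 68 | 64 / 69 / 66 | 61 / 65 / 58 |
| 0.3 | 64 / 68 / 72 | 58 / 63 / 70 | 49 / 53 / 61 |
| 0.5 | 61 / 66 / 80 | 53 / 58 / 78 | 39 / 42 / 70 |

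**No true effect (s = 50%, correlation 0.5).** The paired test rejects 12.5% of the time towards harm and 0.3% towards benefit. The volume model rejects 2.1% and 2.7%.

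**Other shapes at s = 50%, paired against volume model.** Each line gives correlation 0.3, then 0.5.

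- Lognormal gland size: 50 against 64%, and 39 against 72%.
- Lognormal EBL (log-SD 0.6): 54 against 63%, and 43 against 66%.
- Benefit rising by 0.3 SD per SD of size: 50 against 57%, and 40 against 64%.

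**Where adjustment costs.** With a 1-SD gap and zero correlation, power is 66 / 71 / 58%. With the skewed EBL above and no true effect, the volume model's rejection towards benefit reaches about 4% against a nominal 2.5%. The paired test stays near 0.2% in that setting.

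**Pair assignment.** Ten patients in three groups put at least four in one group, so at least 4! × 3! × 3! = 864 pairings are admissible, and 4.2 does not say how to choose among them. The mean difference is the same under every complete pairing. Only its standard error and p-value move.

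**The case against.** **The one-arm restriction is not certain.** The lead-in to 3.1 speaks of entry to the study in general, and 4.2 says "A similar cohort of patients who undergo RALRP without PAE will be treated as a matched control group". Read strictly, section 3 would leave controls with no age range either. This stands: a reader might infer that control glands will be smaller, but the documents give no control sizes, so a gap is a possibility. Size would still be unmatched and unadjusted if the criterion covered both arms.

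**The correlation is unknown.** Section 1.2 gives a direction, not a strength. This also stands. At correlation 0.1 the volume model trails the simpler risk-group model at every share, and the large gains need 0.3 to 0.5.

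**Adjustment may extrapolate.** If the criterion applies to one arm, no PAE patient is available for comparison with a control at or below 40 g except through the fitted line. That is a real limit, and the reason to settle the criterion as well as change the model.

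**The pairing is not an error.** A reader might infer that the missing assignment rule invalidates the t-test. It does not. If pairs are fixed before surgery, type I error holds and the estimate does not depend on the pairing. What remains is a gap in detail.

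**False claims of benefit.** A reader might fear that the planned test favors PAE. Under a smaller-gland control group it does the reverse, since its excess rejections point to harm.

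**Conclusion.** The point holds as a worthwhile improvement to the primary analysis, not as a flaw that invalidates the study. The planned comparison ignores a predictor of blood loss that the protocol names, and the text does not settle whether the size criterion covers controls.

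If control glands are smaller, the bias runs against PAE. At a 50% share it would be about 0.24 SD for correlation 0.3 and 0.40 SD for correlation 0.5. Power would then be about 50% against 61%, and 39% against 70%, for the paired and volume-adjusted analyses. With a weak correlation of 0.1 there is little to choose: about 3 points either way.

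All of this rests on assumed effect size, correlation and size distribution. The proof-of-concept purpose and the planned baseline table lower the stakes, but the table alone does not correct the estimate.

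**What to change.** 1. **Primary EBL analysis.** Name a linear model with treatment, AUA risk group and Visit -1 MRI prostate volume, using every patient with EBL recorded. Report the adjusted between-arm difference with its 95% CI. Keep the matched pairs t-test as a sensitivity analysis.
2. **Which volume.** State that it is the pre-PAE value in the PAE arm and the pre-RALRP value in controls. Section 9.1 allows either procedure to define baseline for PAE patients, and a post-PAE volume would adjust away part of the proposed mechanism.
3. **Measurement and criterion.** State that Visit -1 volume is read the same way in both arms. Reconcile 3.1, 4.2 and 5.1 on whether the >40 g criterion applies to controls. If sizes overlap poorly, say that the adjusted result extrapolates.
4. **Skewness.** Check residuals and prespecify a log-EBL sensitivity analysis.
5. **Minor.** For the sensitivity test, add a one-line rule for assigning a control among PAE patients in the same risk group (for example, the earliest-enrolled unmatched one) and a dated pair list fixed before each control's RALRP.

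The cost is mainly SAP wording, because risk group and the Visit -1 MRI are already scheduled in both arms; consistent volume reads in controls are the one added task. Statistically it costs one degree of freedom against a risk-group model (15 against 16). In the worst case shown, a 1-SD size gap with no prognostic value, it costs 8 to 9 points of power against the paired test. With strongly skewed EBL the false-benefit rate can reach about 4%, which is why item 4 is needed.

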### **9.5.2 Key Secondary Efficacy Outcomes**

#### ***9.5.2.1 Changes in Hemoglobin***

The change in hemoglobin between RALRP post-operative day one (POD1) and baseline (collected on day of RALRP prior to surgery) will be calculated for each patient. Data will be summarized for each time point, as well as the change from baseline, including 95% confidence intervals for the means. Treatment means for the change from baseline will be compared using a matched pairs t-test.

#### ***9.5.2.2 Changes in Hematocrit***

The change in hematocrit between RALRP post-operative day one (POD1) and baseline (collected on day of RALRP prior to surgery) will be calculated for each patient. Data will be summarized for each time point, as well as the change from baseline, including 95% confidence intervals for the means. Treatment means for the change from baseline will be compared using a matched pairs t-test.

#### ***9.5.2.3 Blood transfusions during RALRP***

The analysis of the blood transfusion requirements during RALRP will be performed in two ways. First, patients will be classified as requiring a transfusion or not. Proportions will be summarized, including 95% confidence intervals. Treatments will be compared using an exact binomial sign test. A second analysis will compare the amount of blood transfused between the two groups, where patients who did not receive a transfusion will be assigned a value of zero. This data will be summarized for both treatment groups, including 95% confidence intervals for the means. Treatment means will be compared using a matched pairs t-test.

#### ***9.5.2.4 RALRP Duration***

The duration of the RALRP procedure in minutes will be recorded for each patient. Data will be summarized, including 95% confidence intervals for the means. Treatment means will be compared using a matched pairs t-test.

#### ***9.5.2.5 Length of Hospital Stay for RALRP***

The length of stay (LOS) associated with the RALRP procedure will be calculated for each patient by counting the number of hours spent in the hospital from the time of admission to the time of discharge. Data will be summarized, including 95% confidence intervals for the means. Treatment means will be compared using a matched pairs t-test.

#### ***9.5.2.6 Surgical Margin Assessment***

An analysis of the presence or absence of a complete surgical margin around the entire tumor as determined by histopathology examination post RALRP will be performed. Each patient will be classified as having a complete surgical margin or not, (presence or absence) and proportions will be summarized, including 95% confidence intervals. Treatments will be compared using an exact binomial sign test.

#### ***9.5.2.7 Biochemical Recurrence of Prostate Cancer***

An analysis of the presence or absence of biochemical recurrence of prostate cancer as determined by PSA levels post RALRP at one year follow-up (Visit 9) will be performed. Each patient will be classified as having biochemical recurrence or not, and proportions will be summarized, including 95% confidence intervals. Treatments will be compared using an exact binomial sign test.

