### **2.2 Secondary Objectives**

The key secondary objectives are to assess the outcomes listed below and to compare the results for patients who receive PAE and those that do not:

1. Change in hemoglobin on RALRP post operative day (POD) 1 compared to baseline
2. Change in hematocrit on RALRP post operative day (POD) 1 compared to baseline
3. Change in prostate volume between baseline and Visit 3 (6 weeks  $\pm$  2 weeks post PAE) as determined by MRI in patients who receive PAE
4. Blood transfusion requirements during RALRP
5. RALRP duration in minutes
6. Length of hospital stay for RALRP
7. Presence or absence of a complete surgical margin around the entire tumor as determined by histopathology examination post RALRP
8. Biochemical recurrence of prostate cancer as determined by PSA levels post RALRP at 1 year follow up
9. Return to continence post RALRP as assessed by the pad weight test.
10. RALRP related adverse events
11. Erectile function compared to baseline as assessed by the IIEF post RALRP at 1 year follow up.

Additional secondary objectives are to assess outcomes listed below for patients that receive PAE:

12. Change in PSA between baseline and Visit 3 (6 weeks  $\pm$  2 weeks post PAE)
13. PAE related adverse events
14. Histologic changes in the prostate after PAE

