### **5.6 Visit 5 (12 days +/- 7 days)**

Patients in the PAE group and the Control group will have the following:

- Physical exam including vital signs, weight, and genitourinary evaluation
- Blood and urine laboratory evaluations as at baseline
- Concomitant medications
- Adverse events
- Urinary catheter removal

Cystoscopy and proctoscopy will be performed: 1) if medically indicated, especially if there is pain out of proportion to that which is expected, 2) in all cases of bleeding per rectum, and 3) in cases of hematuria beyond that which is reasonably expected following prostatectomy.**5.7 Visits 6, 7, 8, 9 (3, 6, 9, and 12 months ± 2 weeks for each visit post RALRP)**

Patients in the PAE group will have the following assessments performed:

- Physical exam including vital signs, weight, and genitourinary evaluation
- Prostate Specific Antigen (PSA)
- Expanded Prostate Cancer Index Composite (EPIC) questionnaire
- International Index of Erectile Function (IIEF) questionnaire
- Pad weight test
- Concomitant medications
- Adverse events

Cystoscopy and proctoscopy will be performed: 1) if medically indicated, especially if there is pain out of proportion to that which is expected, 2) in all cases of bleeding per rectum, and 3) in cases of hematuria beyond that which is reasonably expected following prostatectomy.

Patients in the Control group will have the following assessments performed:

- Physical exam including vital signs, weight, and genitourinary evaluation
- Prostate Specific Antigen (PSA)
- Expanded Prostate Cancer Index Composite (EPIC) questionnaire
- International Index of Erectile Function (IIEF) questionnaire
- Pad weight test
- Concomitant medications
- Adverse events

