### **9.6.2 Concomitant Medications**

Concomitant medications data will be presented in the data listings.

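### Biochemical recurrence is classified from the Visit 9 PSA alone, so a recurrence at months 3 to 9 that is treated before Visit 9, or has no Visit 9 PSA, can be lost

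*Combined protocol and SAP*

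**What the plan says.** The objective in Section 2.2 is "Biochemical recurrence of prostate cancer as determined by PSA levels post RALRP at 1 year follow up". Section 9.5.2.7 repeats the time point and names the visit: "as determined by PSA levels post RALRP at one year follow-up (Visit 9"). The rule is binary: "Each patient will be classified as having biochemical recurrence or not, and proportions will be summarized, including 95% confidence intervals". The arms are then compared with an exact binomial sign test on the matched pairs.

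PSA is drawn more often than that. Section 4.2 has controls followed by "assessing PSA, EPIC, and IIEF at months 3, 6, 9, and 12 post RALRP". Section 5.7 covers "Visits 6, 7, 8, 9 (3, 6, 9, and 12 months ± 2 weeks for each visit post RALRP") and lists "Prostate Specific Antigen (PSA") for both groups, and Appendices A1 and A2 agree. Visit 6 is therefore month 3, Visit 7 month 6, Visit 8 month 9 and Visit 9 month 12.

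Section 9.5.2.7 gives the month 3, 6 and 9 values no role. It states no PSA threshold, no confirmation rule, no provision that an earlier recurrence counts, and nothing on further cancer treatment or a missing Visit 9 PSA. Salvage treatment appears only in the background (Section 1.2), where "biochemical recurrence, salvage therapy requirements" are listed as separate long-term outcomes. On treatment data, Section 9.6.2 says only: "Concomitant medications data will be presented in the data listings".

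**The concern.** Recurrence is an event: once it has happened, a later low PSA under treatment does not undo it. A classification that looks at one visit measures PSA status at that visit, which is a different quantity. The two part company for patients who recur early and are treated, and for patients who recur early and have no PSA at month 12.

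Such patients are plausible here. Section 3.1 sets no risk-group limit beyond localized disease, and the matching strata in Section 4.2 include a high-risk group. Under Section 6, withdrawn patients are not replaced and are only encouraged to complete the 12-month evaluations.

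Oncologic benefit is part of the study hypothesis (Section 1.2). Margin status is settled at surgery, so this is the only oncologic outcome assessed during follow-up. The loss for a treated early recurrence runs in one direction, towards no recurrence.

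**Working it through.** The plan gives no recurrence rate, power or effect size for this outcome, so there is no figure of its own to reproduce. The check is first textual, then a matter of scale.

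**1. Does the text mean one visit or all visits?** Section 9.5.2.7 names Visit 9 only. The next two sections, on continence (9.5.2.8) and erectile function (9.5.2.9), list each post-operative time point they use. The authors thus name several visits when they mean several. The plain reading is Visit 9 alone.

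**2. Result of the Visit 9 rule, whatever threshold is chosen**

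| Patient | Visit 9 rule | Event by 1 year |
|---|---|---|
| PSA rises at months 3–9, untreated, still raised at Visit 9 | recurrence | recurrence |
| PSA rises at months 3–9, treated, still above threshold at Visit 9 | recurrence | recurrence |
| PSA rises at months 3–9, treated, below threshold at Visit 9 | no recurrence | recurrence |
| PSA rises at months 3–9, no Visit 9 PSA | missing (no rule stated) | recurrence |

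Rows 3 and 4 are the problem. Supplying a threshold alone cures neither.

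**3. Size per patient (10 per arm, Section 4).**
- Misclassified: k/10 becomes (k − 1)/10, a fall of 10 points.
- Missing and dropped from the denominator (an assumption): k/10 becomes (k − 1)/9, a fall of (10 − k)/90. That is 10.0 points for k = 1, 8.9 for k = 2 and 7.8 for k = 3.

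**4. Effect on the sign test.** A misclassified recurrence turns a (yes, no) pair into (no, no), removing a discordant pair, or a (yes, yes) pair into (no, yes), creating one. A missing result takes the pair out of the test. At an assumed two-sided 0.05 level (none is stated), six discordant pairs all one way give p = 2 × 0.5^6 = 0.031, and five give p = 2 × 0.5^5 = 0.0625.

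**5. Illustration on assumed inputs.** Let r be the true proportion recurring by 12 months, e the share of those treated before Visit 9, and s the share of the treated whose PSA is below threshold at Visit 9. The expected Visit 9 proportion is r(1 − e·s), and the chance that at least one of 10 patients in an arm is missed is 1 − (1 − r·e·s)^10.

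| r | e | s | Visit 9 proportion | P(at least 1 of 10 missed) |
|---|---|---|---|---|
| any | any | 0 | r (no loss) | 0 |
| 0.10 | 0.25 | 0.5 | 0.0875 | 0.118 |
| 0.20 | 0.50 | 1 | 0.10 | 0.651 |
| 0.30 | 0.75 | 1 | 0.075 | 0.922 |

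Across r = 0.10–0.30, e = 0.25–0.75 and s = 0–1, the Visit 9 rule shows between 25% and 100% of the true proportion. None of these inputs comes from the documents.

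**6. Timing.** Section 9.1 runs all analyses on a database locked once every patient has completed Visit 7 (month 6), died or been lost. Section 9.5.2.7 needs a PSA from month 12. As written, the lock can precede the value that the rule depends on.

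**The case against.** The strongest reply is that nothing in the plan says a treated recurrence counts as no recurrence. A reader might infer that it always will. The documents do not support that: the PSA must rise by months 3 to 9, treatment must start before Visit 9, and the Visit 9 value must then fall below a threshold that the plan never sets. A patient who is untreated, or treated but still raised, is classified correctly. This stands, and the point is about what can happen.

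The plural in PSA levels leaves a little room to read the rule as covering all values up to one year. The named visit and the wording of the neighbouring sections weigh against it. If both readings are open, two analysts could classify the same patient differently, which is also a reason to change the text.

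It can be said that the real gap is the missing definition of recurrence. That gap exists, but filling it with a threshold would leave rows 3 and 4 of the table unchanged.

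A reader might also infer that the loss favours the PAE arm because embolization delays surgery. The documents do not show this. Controls may also wait about 12 weeks from baseline (Section 5.5; Appendix A2 says 12 ± 2 weeks), and the mechanism applies to both arms. Nor can one such error reverse a discordant pair.

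Finally, this is a secondary outcome in a proof-of-concept study without a sample size calculation (Section 9.2). The exact 95% interval is 0.3% to 44.5% for 1 of 10 and 2.5% to 55.6% for 2 of 10, so one patient will seldom change a formal conclusion. That limits the importance, but is no reason to keep a rule that can discard observed events. Section 6 makes a missing Visit 9 PSA less likely without excluding it.

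**Conclusion.** The concern holds in a limited form. On its plain reading, the single-visit rule can label a treated early recurrence as recurrence-free and can turn a documented recurrence into a missing value. Each such patient costs an arm up to 10 points. The number affected is unknown and may be zero; the illustration rests wholly on assumed rates of recurrence, early treatment and PSA suppression. No difference between arms is claimed. It is worth correcting because the misclassification runs one way and the PSA values needed to avoid it are already scheduled.

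**What to change.** In Sections 2.2 and 9.5.2.7, define the outcome as recurrence by 1 year: a PSA meeting one pre-specified threshold at any of Visits 6 to 9, or the start of further prostate cancer treatment for rising PSA. Once met, it stands, whatever the Visit 9 value and even if the patient withdraws. State how a patient with no recurrence so far and no Visit 9 PSA is classified.

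If confirmation is required, use the next scheduled PSA or the start of treatment, and state how a first rise at Visit 9 is handled, since no later study PSA is scheduled to confirm it. Reconcile the lock after Visit 7 in Section 9.1 with the use of a Visit 9 PSA.

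The cost is SAP wording plus at most one CRF item. It would be too much to say that everything needed is already collected: PSA and concomitant medications are, but the visit lists do not explicitly capture further cancer treatment such as radiotherapy, and adverse event records would show it only if the PSA rise were itself reported as an event.
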